11.4 Analysis of Translational Medicine Endpoints

Aim: To identify the relationship between expression of markers of epithelial mesenchymal transition in the primary bladder tumor with local tumor stage, the burden of lymph node metastases, and the likelihood of disease recurrence among patients undergoing cystectomy for muscle invasive bladder cancer.

Tumor marker expression will be measured as a function of proportion of cells staining and intensity of staining (IHC studies) and/or relative level of mRNA expression (compared to internal controls). Associations between marker expression and nodal status (positive vs negative, low disease burden versus high disease burden), and neoadjuvant chemotherapy will be tested using chi square test. Kaplan Meier estimates of survival and DFS based on marker expression will be performed and corresponding survival and DFS curves will be compared using log rank testing. Cox proportional hazards regression analysis will be performed to estimate hazard ratios for progression free survival. Those analysis will be repeated, stratified by whether patients received

neoadjuvant and adjuvant chemotherapy. Where associations look different by strata, formal tests of interaction will be performed in order to assess markers associated with chemoresistance.

If we assume that 70% of patients will have adequate tissue samples available based on prior SWOG experience with surgical trials, then we will have 396 samples (198 per arm). The following table provides estimate of the minimally detectable hazard ratio for disease-free survival for those with the tissue marker of interest vs. those without. These calculations assume 5 years of accrual, 3 additional years of follow-up, median DFS of 3-year in those with the marker, a two-sided alpha=0.05 and 80% statistical power. Similar survival hazard ratios can be detected with two additional years of follow-up. These calculations also assume there is no interaction between the marker of interest and the randomized treatment assignment (type of lymph node dissection).

	Prevalence of Tissue Marker		
	10%	20%	30%
DFS Hazard Ratio for Those with versus Those without the Marker of Interest	1.82	1.57	1.50

In some cases, there may be a combination of markers that have a multiplicative effect on the risk of relapse or death. In addition to assessing multivariate proportional hazards regression models, we will also develop classification and regression trees to assess these potential multiplicative effects among the markers.

Although statistical power is lower, we also would like to evaluate whether some tissue markers are predictive of DFS and survival in those who receive neoadjuvant chemotherapy compared to those who did not. In other words, we will evaluate the marker by chemotherapy interaction, at least in a preliminary fashion. If we assume the following distribution of a tissue marker and neoadjuvant chemotherapy:

Tissue Marker Status (30% prev.)	Prior chemotherapy	Exposure to chemotherapy	Neoadjuvant
Yes			No
Absent	35%	HR = .48	35% HR = 1.0
Present	15%		15%

(and assume 55% 3-year DFS for those without the marker) and we specify a two-sided alpha=0.05 then there will be 80% statistical power to detect a difference in DFS hazard ratios of 1.0 for the tissue marker absence vs. presence in those without neoadjuvant chemotherapy versus a HR = 0.48 for the tissue marker absence vs. presence in those with prior chemotherapy, suggesting a predictive tissue marker for chemotherapy resistance.

This analysis assumes that type of nodal surgery does not have an impact, and the randomized groups are pooled together.

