An extended node dissection in patients undergoing cystectomy for bladder cancer may offer a survival benefit compared to a standard node dissection via more complete tumor eradication, improved staging and thus identifying patients who may benefit from adjuvant chemotherapy, or other theoretical mechanisms. In order to optimize the benefits of an extended node dissection through improved nodal staging, all patients with node metastasis will be strongly advised to receive peri-operative chemotherapy which is currently considered a standard of care in locally advanced urothelial bladder cancer. In addition and in accordance with standard of care, chemotherapy will be strongly recommended for patients found to have advanced pathologic stage (pT3-T4) at cystectomy. Failure to include this stipulation in the trial design could result in biased administration of adjuvant chemotherapy, influenced by which arm the patient was randomized to, and lead to non-informative results.

A poll of centers of excellence suggest that a 10-12% improvement in 3-year DFS (65-67%) for patients in extended lymphadenectomy would be meaningful and establish extended node dissection as the standard of care in this patient population

Since the introduction of MVAC chemotherapy in the 1980s, little progress has been made in improving survival for patients with advanced bladder cancer. Despite a significant improvement in overall survival with administration of peri-operative chemotherapy, the mortality rate for patients undergoing radical cystectomy for UCB approaches 50%. A properly performed lymph node dissection may provide a significant improvement in survival for these patients. Currently the boundaries of a pelvic node dissection for patients undergoing radical cystectomy for UCB are not clear and the urologic community has failed to define a standard template. The literature is replete with various proposed definitions. Defining, a standard nodal dissection for this disease is

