7.1 Timing of Randomization

Randomization will be done at the time of surgery after the exploration in order to eliminate any bias in interpretation of the findings of the intra-operative exploration and to minimize drop-outs due to a positive finding of metastatic disease outside the standard node dissection template. After surgical exploration of the abdomen and pelvis and the absence of visceral metastatic and gross positive nodes in any of the extended template fields, surgery will then proceed according to randomization assignment.

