7.3 Adherence to Recommendations for Adjuvant Chemotherapy

For patients who did not receive neoadjuvant chemotherapy, post operative adjuvant chemotherapy for pT any, N+ or pT3-4, N0 is strongly recommended but not required and will be left up to the treating physician. The Study Chairs will review the records of all patients enrolled to assess adherence to this recommendation. Non-compliance with this recommendation will be addressed by inquiry with the site physicians and coordinators.

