10.3 Disease-Free Survival

From date of randomization to date of first documentation of relapse/recurrence or death due to any cause. Patients last known to be alive without report of relapse/recurrence are censored at date of last contact.

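### Section 11.4 compares marker effects by adjuvant chemotherapy received without adjusting for pathologic stage, so a marker that only tracks stage can produce a false interaction

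*Combined protocol and SAP*

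**What the plan says.** Section 11.4 plans Kaplan-Meier, log-rank and Cox analyses of survival and DFS by marker expression. It then runs them again in subgroups defined by receipt of "neoadjuvant and adjuvant chemotherapy. Where associations look different by strata, formal tests of interaction will be performed". The stated purpose is to find markers of chemoresistance.

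Four other places bear on this:
- Section 7.1 sets the time of randomization: "Randomization will be done at the time of surgery after the exploration". Section 10.3 runs DFS "From date of randomization to date of first documentation of relapse/recurrence or death due to any cause". Adjuvant chemotherapy therefore starts after the DFS clock does.
- Section 7.3 says that, in patients without neoadjuvant chemotherapy, "post operative adjuvant chemotherapy for pT any, N+ or pT3-4, N0 is strongly recommended but not required". The decision is left to the treating physician.
- The aim of Section 11.4 is "To identify the relationship between expression of markers of epithelial mesenchymal transition in the primary bladder tumor with local tumor stage", and also with nodal burden and recurrence. Objective 1.3a is similar.
- Section 2.0 warns that, without such a recommendation, the design "could result in biased administration of adjuvant chemotherapy, influenced by which arm the patient was randomized to".

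For the adjuvant strata, Section 11.4 names no stage covariate, no restriction to patients with the indication, no landmark and no time-dependent covariate. The multivariate models it mentions later concern combinations of markers. Pathologic stage enters a prognostic model only in the separate pre-metastatic-niche plan in Appendix 18.2.

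**The concern.** Neoadjuvant chemotherapy is a baseline factor; adjuvant chemotherapy is not. Under Section 7.3 the adjuvant stratum will be nearly all high-stage, while the other stratum mixes low-stage patients with untreated high-stage patients. Within the mixed stratum, a marker that is commoner in high-stage disease separates patients by stage and so appears prognostic. Within the adjuvant stratum there is little stage left to separate, so the same marker appears inert. The difference between strata is then produced by who was selected for treatment. A predictive claim about a marker and chemotherapy could be published on that basis.

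**Working it through.** **Step 1. The plan's own figure.** The only interaction powered in Section 11.4 is marker by neoadjuvant chemotherapy: cells of 35%, 15%, 35% and 15%, 3-year DFS of 55% without the marker, hazard ratios (absent versus present) of 0.48 with and 1.0 without neoadjuvant chemotherapy, two-sided alpha 0.05, and 80% power.
- Samples: 0.7 × 564 = 394.8; the plan uses 396.
- Hazard without the marker: −ln(0.55)/3 = 0.199 per year. With 5 years of uniform accrual and 3 more of follow-up, expected events in the four cells are 90.3, 52.2, 90.3 and 38.7.
- SE = √(1/90.3 + 1/52.2 + 1/90.3 + 1/38.7) = 0.259.
- Power = Φ(|ln 0.48|/0.259 − 1.96) = 80.9%.

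The stated 80% reproduces. No figure is given for an interaction with adjuvant chemotherapy.

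**Step 2. Relevant sample.** The same layout puts 35% + 15% = 50% of patients in the neoadjuvant group. That leaves 0.5 × 396 = 198 to whom Section 7.3 can apply (the plan's per-arm number happens to be the same). Using all 396 is an upper bound.

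**Step 3. The mechanism by hand.** Assumptions not in the documents: half of patients are high-stage, stage HR is 2.5, uptake is 60% in high-stage patients still event-free at month 3, and neither marker nor chemotherapy has any true effect. With a mean hazard of 0.199, the low-stage hazard is 0.199/1.75 = 0.114 and the high-stage hazard 2.5 times that, 0.284.
- Of 99 high-stage patients, 99 × 0.6 × exp(−0.284 × 0.25) ≈ 55 are treated and 44 are not. The no-adjuvant stratum is 99 low-stage plus 44 high-stage.
- Strong link (marker in 45% of high-stage and 15% of low-stage patients): within that stratum about 57% of marker-positive and 22% of marker-negative patients are high-stage. Mean hazards are about 0.211 and 0.152, a ratio of about 1.39.
- Weak link (35% and 25%): about 38% and 28% are high-stage, and the ratio is about 1.11.
- In the adjuvant stratum all are high-stage, so the ratio is 1.00.

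This ignores early events. Simulation of the strong link gave marker HRs of about 1.47 without and 1.03 with adjuvant chemotherapy.

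**Step 4. Rejection rate of the nominal 5% test under the null.** Same assumptions, 1,500 trials per cell; a separate set of runs with a strong, moderate and weak link is in brackets.

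| Marker prevalence, high / low stage | n = 198 | n = 396 |
|---|---|---|
| 45% / 15% | 13.9% (about 15%) | 24.8% (about 23%) |
| 40% / 20% | 8.1% (about 8%) | 12.5% (about 14%) |
| 35% / 25% | 5.2% (about 5%) | 6.3% (about 6%) |

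A run of only 150 trials at n = 396 gave about 30% for the strong link, with a Monte Carlo standard error of √(0.3 × 0.7/150) = 3.7 points.

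**Step 5. Different assumptions, and which part drives it.** This check used 4,000 trials per scenario, n = 198, marker prevalence 30%, high stage in 75% of marker-positive and 45% of marker-negative patients, stage HR 3.0, and uptake of 60% in high and 5% in low stage.
- Rejection rate 11.0%; median marker HR 1.44 without and 1.07 with adjuvant chemotherapy.
- Stage selection alone: 9.8%. Survivorship alone (treated patients must be event-free at month 3, marker unrelated to stage): 4.1%. Neither: 4.8%.
- Weak link (65% versus 50%): 5.3%. Harsher case (80% versus 40%, uptake 80%): 19.8%.

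**Step 6. After correction.** With stage in the model the rate is 4.9%, and 6.4% in the harsher case. A 3-month landmark restricted to high-stage patients gives 4.9% and 6.2%, so it does no better on this test.

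**The case against.** The strongest reply is that this is a single conditional clause in an exploratory analysis of banked tissue, and Section 15.0 makes that work dependent on funding. The only powered interaction uses neoadjuvant chemotherapy, is described as preliminary, and involves a treatment given before randomization. The marker-stage link, the proportion indicated, the stage hazard ratio and the uptake are all assumed, and with a weak link the test stays near 5%. All of this stands. It limits the size and importance of the point, but it does not supply the missing stage adjustment.

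A reader might also infer three stronger things that the material does not support:
- That survivorship (immortal time) is what creates the false interaction. Alone it did not inflate the test (4.1%). It would bias a direct comparison of adjuvant with no adjuvant chemotherapy: early events alone make an inert treatment look like an HR of about 0.80-0.86 among indicated patients. Section 11.4 does not plan that comparison.
- That the analysis would falsely announce chemoresistance. Section 11.4's resistance pattern is a marker that matters with chemotherapy and not without. The artefact here runs the other way and resembles chemosensitivity.
- That a rate near 30% is to be expected. It combines the upper-bound sample with the strong link, in a small run.

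**Conclusion.** The concern holds in direction. Followed as written, the adjuvant part of Section 11.4 can yield a marker-by-chemotherapy interaction where none exists, through selection by pathologic stage. The size is uncertain: about 5% to 15% rejection at roughly 198 patients, and about 6% to 25-30% at 396, under inputs the documents do not state. Testing only where strata look different is a further source of false positives, not counted in these rates. The finding is confined to an exploratory analysis; it touches neither the primary DFS comparison nor the neoadjuvant interaction, whose 80% power reproduces.

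**What to change.** In Section 11.4, keep the neoadjuvant strata as they are. Replace the adjuvant stratification with an analysis, labelled exploratory, in patients who had no neoadjuvant chemotherapy. Fit a Cox model with marker, adjuvant chemotherapy, their interaction, pT and pN. Where the start date is recorded, enter adjuvant chemotherapy as a time-dependent covariate. A landmark analysis among pT3-4 or N+ patients can serve as a sensitivity analysis.

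The cost is small. pT and pN should be on the cystectomy pathology report already submitted under Section 14.4b; the sponsor should confirm that the start date is captured. There is slightly more modelling and some loss of precision.

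The landmark should not be the main analysis. At n = 198 it keeps about 92 patients, with an interaction SE of about 0.52, so 80% power needs a ratio near exp(−2.80 × 0.52) = 0.23. It also counts later starters as untreated, which the simulations did not test.

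### Section 11.4 makes marker-by-chemotherapy interaction tests depend on how the strata look, contradicts its own unconditional plan for the neoadjuvant interaction, and sets no multiplicity control

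*Combined protocol and SAP*

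**What the plan says.** Section 11.4 first describes marker analyses of DFS and survival by Kaplan-Meier, log-rank and Cox methods. It then adds: "Those analysis will be repeated, stratified by whether patients received" neoadjuvant and adjuvant chemotherapy. The next sentence sets the rule at issue: "Where associations look different by strata, formal tests of interaction will be performed in order to assess markers associated with chemoresistance". It gives no statistic or threshold for looking different and no significance level.

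Later in the same section the neoadjuvant interaction is treated differently: "we will evaluate the marker by chemotherapy interaction, at least in a preliminary fashion". This statement has no look-first condition. It comes with a layout of marker status by neoadjuvant chemotherapy (30% marker prevalence, half the patients treated), "and we specify a two-sided alpha=0.05 then there will be 80% statistical power" and an effect of HR 1.0 without neoadjuvant chemotherapy "versus a HR = 0.48 for the tissue marker absence vs. presence in those with prior chemotherapy".

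Section 11.3 promises adjustment for multiple comparisons for the surgical endpoints. Section 11.4 makes no such promise. Appendix 18.2 lists nine antibodies for immunohistochemistry, plus PCR and microRNA targets.

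**The concern.** The stratum estimates that decide whether an interaction test is run also determine its result. With no true interaction, the tests that get run are those whose observed difference is already large, so more than 5% of them reach p < 0.05. How many more depends on what looking different means, and the plan leaves that open. Nor does it require the markers that did not prompt a test to be counted or reported, so a reader of the results may not know how many were examined.

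The stated purpose is to name markers of chemoresistance, which then become candidates for further work. A p-value from this route cannot be calibrated, and the power figure in the same section belongs to a different procedure.

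**Working it through.** **Inputs from Section 11.4.** 396 samples; marker-by-chemotherapy cells of 35%, 15%, 35% and 15%; 55% 3-year DFS without the marker; absent-versus-present HR 0.48 with neoadjuvant chemotherapy and 1.0 without; two-sided 0.05. Assumed: exponential DFS with uniform accrual, and the 5 years of accrual plus 3 years of follow-up, stated for the main-effect table, carried over to the interaction.

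**1. The plan's 80%.**
- Hazard λ = −ln(0.55)/3 = 0.199 per year.
- P(event) = 1 − [exp(−3λ) − exp(−8λ)]/(5λ) = 0.652. At hazard λ/0.48 it is 0.879.
- Expected events: 396 × 0.35 × 0.652 = 90.3 (marker absent, each stratum); 396 × 0.15 × 0.879 = 52.2 (present, chemotherapy); 396 × 0.15 × 0.652 = 38.7 (present, no chemotherapy).
- SE of the log ratio of HRs = √(1/90.3 + 1/52.2 + 1/90.3 + 1/38.7) = 0.259.
- Power = Φ(−ln(0.48)/0.259 − 1.96) = Φ(2.833 − 1.96) = 80.9%.

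The stated power reproduces for a test that is always run.

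**2. Error among tests performed, with no interaction.** P(p < 0.05 | tested) = P(p < 0.05 and triggered)/P(triggered). With no marker effect, the stratum SE is √(1/38.7 + 1/90.3) = 0.192 and the interaction SE is 0.192 × √2 = 0.272. The three triggers below are assumptions, evaluated by simulation from the normal approximation.

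| Assumed meaning of looking different | Tested | Tested and p < 0.05 | Significant among tested |
|---|---|---|---|
| Significant in one stratum only | 9.5% | 3.1% | 33% |
| Ratio of HRs above 1.5, either way | 13.6% | 5.0% | 37% |
| Opposite directions | 50% | 4.9% | 10% |

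The second row has a closed form: ln(1.5)/0.272 = 1.49, P(|Z| > 1.49) = 0.136, and 0.05/0.136 = 37%.

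A main effect changes these rates. With a marker HR of 1.5 in both strata, marker-present events rise to 46.8 per stratum. The stratum SE is then √(1/46.8 + 1/90.3) = 0.180 and the interaction SE 0.255. The ratio trigger gives ln(1.5)/0.255 = 1.59, P = 0.111, and 0.05/0.111 = 45%.

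**3. Error per marker examined.** The third numeric column shows it: 3.1%, 5.0% and 4.9%. A null marker must both prompt the test and reach p < 0.05, so screening cannot raise this above 5%.

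**4. Chance of finding the planned effect.** Under HR 0.48 versus 1.0 (stratum SEs 0.174 and 0.192), the probability that the test is both triggered and significant is 81% for a ratio above 1.5, 78% for significance in one stratum only, and 49% for opposite directions. The last is low because a true HR of 1.0 in the untreated stratum falls on either side of 1 about equally often.

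**5. Multiplicity.** Nine antibodies, one test each at 0.05, if independent: 1 − 0.95⁹ = 37% family-wise error.

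**The case against.** The strongest reply is that the look-first rule creates no extra false positives. A null marker is declared significant no more often than if every marker were tested, and for a trigger on the size of the standardised difference with a cutoff below 1.96 the list of significant interactions is the same either way. This stands. Testing everything without a multiplicity adjustment would give as many false positives or more.

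A reader might also infer that interactions are tested only after looking. The documents do not support that for neoadjuvant chemotherapy, because the later paragraph of Section 11.4 plans that test unconditionally. Nor is the 80% figure wrong: it belongs to that unconditional test and reproduces.

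The triggers in the table are assumed, so the percentages are not the plan's. The plan itself calls this evaluation preliminary and lower powered, and Section 15.0 makes the tissue optional and the studies dependent on funding. Nothing says that stratified results will be withheld.

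What remains is that one section gives two rules for the same interaction, one of them undefined; the adjuvant interaction has only the undefined rule; and no rule covers the number of markers tested.

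**Conclusion.** The concern holds in this limited form. The two statements in Section 11.4 conflict for neoadjuvant chemotherapy, and the look-first rule leaves the p-values of the tests performed uncalibrated. About 10% to 37% of performed tests would be significant with no interaction and no main effect under the three triggers tried, and up to 45% with a main-effect HR of 1.5. Other triggers can give more.

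A reader might take these figures as the chance that a reported significant interaction is false. They are not: they are conditional on the marker having been tested and having no interaction, and the share of false claims also depends on how many markers are truly null, which the documents do not give. The more direct sources of unreliable claims are the uncounted markers and the missing multiplicity rule. The 37% family-wise figure assumes nine independent tests.

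Severity is minor to moderate. The primary DFS analysis and the OS analysis are unaffected.

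**What to change.** In Section 11.4:
- Delete the opening condition of the interaction sentence, so that it agrees with the later paragraph.
- List the EMT markers and the chemotherapy comparison or comparisons, and fit the marker-by-chemotherapy interaction for every listed marker whatever the stratum results show.
- Report all interaction estimates with confidence intervals.
- Apply Benjamini-Hochberg over the full set, and label the results exploratory.

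This restores a 5% level per test before adjustment and makes the stated power apply to the procedure used.

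The cost is wording and a longer results table, with no extra patients or assays. Power per marker after adjustment will be below the 80% stated at an unadjusted 0.05. With nine tests the Benjamini-Hochberg threshold lies between 0.05/9 = 0.0056 and 0.05. At 0.0056 (critical value 2.773), power for the planned effect is Φ(2.833 − 2.773) = 52%, so the adjusted figure lies between 52% and 81%. The plan should say so.

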11.0 STATISTICAL CONSIDERATIONS

11.1 Accrual Goal

We anticipate that 113 eligible patients will be randomized per year to this study on a group-wide basis. We will also assume that 10 percent of enrolled patients will be found to be clinically or pathologically ineligible and hence, not randomized so our Step 1 sample size will be inflated to account for this. Based on an extensive review of the contemporary literature (see [Section 2.0, Table 1](#)), we estimate that 3-year disease free survival (DFS) for patients at increased risk for pelvic and iliac node metastasis undergoing a standard pelvic lymphadenectomy is 55%. A poll of centers of excellence suggest that a 10-12% improvement in 3-year DFS (65-67%) for patients in extended lymphadenectomy would be meaningful and establish extended node dissection as the standard of care in this patient population. Assuming exponential survival, 5 years of patient accrual, 3 additional years of follow-up and a sample size of 564 eligible patients (282 per arm), the study has 85% power to detect a 28% reduction in the hazard rate of progression or death with extended lymph node dissection compared to limited

dissection (hazard ratio 0.72). This corresponds to an improvement in 3-year DFS from 55% to 65% or alternatively median DFS would be extended from 3.5 to 4.8 years if the DFS distributions are exponential. We will use a one sided stratified log rank test with $\alpha = 0.025$, and the analysis will be intent-to-treat.

Assuming an ineligibility rate of 10%, total accrual (eligible + ineligible patients) to the initial step is expected to be 620 patients.

As a secondary endpoint, overall survival is also of great interest. If extended lymph node dissection is found to be statistically significantly better than standard lymph node dissection with respect to DFS, then an analysis of the survival endpoint will follow. We will allow for three more years of follow-up after the primary analysis has been conducted to assess potential survival differences. If we assume that the standard arm has 5-year survival of 55% then we will have 83% statistical power to detect a hazard ratio of 0.72 (55% vs. 65% survival at 5 years) using a one-sided stratified logrank test with alpha=0.025.

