expression) relative those with a low biomarker expression level. These effect sizes apply equally to the training and validation subsets since the sample size will be the same for both. The designation of "high" and "low" biomarker expression levels will be based on the cutoffs designated in the training cohort. These calculations assume 5 years of accrual, 3 additional years of follow-up, median 3-year DFS of 50% in those with "high" biomarker expression, a two-sided alpha of 0.05, and 80% statistical power. These calculations further assume that there is no interaction between the marker of interest and the randomized treatment assignment (type of lymph node dissection). Because all currently enrolling patients are being offered participation in the banking of their lymph node tissue, there will be no loss of sample size for this recently activated trial.

In some cases, there may be a combination of biomarkers that have a multiplicative effect on the risk of relapse. Classification and regression trees to assess the potential multiplicative effect amongst markers and form prognostic groups based on these algorithms will be explored. Prognostic models using traditional clinical factors such as clinical stage,

pathologic stage, age, receipt of neoadjuvant chemotherapy and performance status to predict disease-free survival will be developed in the training set and the area under the curve (AUC) will be calculated in the validation set. (43) Then, the model that also incorporates markers of the pre-metastatic niche (identified in the training set) will also be added to the model and the AUC will again be estimated. A comparison of the traditional AUC to the niche AUC will be made to evaluate whether these biomarker expression factors contribute to the DFS prognosis in this patient population.

Bibliography for 18.2

- 1 Fidler, I.J., Critical factors in the biology of human cancer metastasis: twenty-eighth G.H.A. Clowes memorial award lecture. *Cancer Res* 50(19):6130-8, 1990.)

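### Minor, free improvement: Section 11.4 pools the arms for the exploratory marker-by-neoadjuvant-chemotherapy analysis as if nodal surgery had no effect, and nothing checks the no-interaction assumption used for the other marker calculations

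*Combined protocol and SAP*

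**What the plan says.** Three statements in the combined protocol and SAP bear on how the randomized arm enters the marker work.

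- **Main marker table (Section 11.4).** "These calculations also assume there is no interaction between the marker of interest and the randomized treatment assignment". The sample is described thus: "then we will have 396 samples (198 per arm").
- **Marker-by-neoadjuvant-chemotherapy calculation (Section 11.4).** This is introduced as preliminary. It claims 80% power at two-sided 0.05 for a marker hazard ratio (absent vs present) of 0.48 with prior chemotherapy against 1.0 without, and closes: "This analysis assumes that type of nodal surgery does not have an impact, and the randomized groups are pooled together".
- **Niche-marker table (Appendix 18.2, part b).** "These calculations further assume that there is no interaction between the marker of interest and the randomized treatment assignment".

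The trial itself (Section 11.1) has "85% power to detect a 28% reduction in the hazard rate", a hazard ratio of 0.72.

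Neither Section 11.4 nor Appendix 18.2 mentions stratifying or adjusting a marker analysis by randomized arm, or testing marker by arm. Section 11.4 does plan to repeat the marker analyses within neoadjuvant and adjuvant chemotherapy strata, with interaction tests where the strata look different.

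**The concern.** If extended dissection works as the design supposes, a calculation that gives it no effect expects too many events and overstates its power. The no-interaction assumption is stated for both marker tables, yet nothing in the plan would show whether it fails. Arm is also the only randomized contrast in the trial. The interactions that are planned involve chemotherapy, which is not randomized: neoadjuvant treatment is permitted before registration (Section 5.2), and adjuvant treatment is left to the treating physician (Section 7.3).

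At stake are a few points of power in an exploratory calculation, and an unused chance to check a stated assumption with data that will be collected anyway.

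**Working it through.** **Inputs.** From 11.4: 396 samples; marker-by-chemotherapy cells of 35/15/35/15%; 55% 3-year DFS without the marker; hazard ratios 0.48 and 1.0; two-sided 0.05; 5 years of accrual plus 3 of follow-up (stated for the main marker table, assumed here for the interaction too). From 11.1: arm hazard ratio 0.72, exponential DFS.

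**Formulas.** With uniform accrual, the probability of an event at hazard λ is p(λ) = 1 − [exp(−3λ) − exp(−8λ)]/(5λ). For an interaction, SE = √(sum of 1/events over the four cells) and power = Φ(|ln ratio|/SE − 1.96).

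**1. The plan's own figures.** λ₀ = −ln(0.55)/3 = 0.1993 per year, so p = 0.652. As a check on the method, 282 × 0.652 = 183.8 control-arm events, against the 184 in Section 11.2. For the interaction, the marker-present chemotherapy cell has hazard λ₀/0.48 and p = 0.879.

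- Expected events: 90.3 (absent, chemotherapy), 52.2 (present, chemotherapy), 90.3 (absent, none), 38.7 (present, none); total 272.
- SE = 0.259; |ln 0.48| = 0.734; 0.734/0.259 = 2.833.
- Power = Φ(2.833 − 1.96) = 80.9%, against the stated 80%.

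**2. The same calculation with arm hazard ratio 0.72.** Half of each cell has its hazard multiplied by 0.72, giving p = 0.536 at the base hazard and 0.788 in the raised cell.

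- Expected events: 82.3, 49.5, 82.3, 35.3; total 249.
- SE = 0.270; 0.734/0.270 = 2.72; power = 77.6%.

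The loss is 80.9 − 77.6 = 3.3 points, and it comes from about 22 fewer events.

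**3. Does pooling itself do harm?** Simulated Cox models with arm hazard ratio 0.72 (interaction: 1,500 trials per scenario; marker main effect: 2,000 datasets, 396 samples, 30% prevalence, marker hazard ratio 1.5):

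| | Pooled | Stratified by arm |
|---|---|---|
| Interaction: ratio of hazard ratios (true 2.08) | 2.09 | 2.11 |
| Interaction: power | 78.3% | 78.7% |
| Interaction: type I error | 4.7% | 4.3% |
| Marker main effect: mean log hazard ratio (true 0.405) | 0.400 | 0.405 |
| Marker main effect: power | 85.4% | 86.0% |

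A separate log-rank simulation gave 85.0% pooled and 85.7% stratified, with type I error 5.0% either way. Stratifying gains under 1 point of power. The pooled estimate is hardly attenuated, and the test keeps its level.

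**4. What a marker-by-arm test could detect.** Assume 396 samples, equal arms, base hazard λ₀, arm hazard ratio 0.72 in marker-negative patients, no marker effect on the standard arm, two-sided 0.05 and 80% power. The detectable ratio solves ln(ratio) = (1.96 + 0.84) × SE.

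| Prevalence | Events (standard −, standard +, extended −, extended +) | SE | Detectable ratio |
|---|---|---|---|
| 30% | 90.3, 38.7, 74.3, 47.1 | 0.268 | 2.1 |
| 20% | 103.2, 25.8, 84.9, 32.5 | 0.302 | 2.3 |
| 10% | 116.2, 12.9, 95.5, 17.6 | 0.392 | 3.0 |

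At 30% prevalence this is close to the 1/0.48 = 2.08 planned for the chemotherapy interaction. Appendix 18.2 lists nine antibodies, seven mRNA targets and four miRNAs. A Bonferroni correction over those 20 raises the 30% figure to exp[(3.02 + 0.84) × 0.266] ≈ 2.8 (SE here with a marker hazard ratio of 1.5 in both arms).

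**The case against.** The strongest reply is that this is a harmless simplification. The no-effect statement belongs to one calculation that the plan itself calls preliminary. The two marker tables assume only no interaction, which is fully compatible with an arm hazard ratio of 0.72. Arm is randomized, and Section 6.0 balances it on neoadjuvant chemotherapy, so it does not confound these associations. All of this stands, and the simulations bear it out.

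It can also be said that no translational objective in Section 1.3 asks which patients gain from extended dissection, so leaving out a marker-by-arm test is not an error. That stands too: it is a missed opportunity. The test would be weak at low prevalence and weaker still after multiplicity adjustment. It is free of confounding only if tissue, expected from 70% of patients and submitted after randomization, is available independently of arm.

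Appendix 18.2 introduces its model covariates by example ("Prognostic models using traditional clinical factors such as clinical stage"), and the multivariable models in 11.4 name no covariates, so silence about arm is not exclusion.

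The two arms do ascertain nodes differently, which might suggest that the marker-by-nodal-status tables need a Mantel-Haenszel test by arm. When simulated, that test gained essentially nothing (82.3% power unstratified, 82.3–82.4% stratified).

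What the reply does not answer is that the no-interaction assumption goes unchecked, and that the 80% power figure is slightly optimistic if the trial succeeds.

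**Conclusion.** A minor point that holds in a limited form. The no-effect assumption for the exploratory chemotherapy interaction differs from the design hazard ratio and costs about 3 points of stated power (80.9% to 77.6%). Pooling as such costs under 1 point. The no-interaction assumption behind the other marker calculations is not checked.

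A reader might infer three stronger things that the documents do not support:

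- **That the plan contradicts itself.** The 0.72 is an alternative hypothesis, and the no-effect statement is a planning simplification for a single calculation.
- **That stratifying by arm is needed for valid marker results.** Type I error is held and bias is negligible without it.
- **That neoadjuvant chemotherapy is the only predictive factor examined.** Section 11.4 also plans adjuvant-chemotherapy strata with interaction tests.

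The figures assume exponential DFS, the main table's accrual and follow-up, 55% 3-year DFS for marker-absent patients with and without chemotherapy, and the same 55% on the standard arm when 0.72 is applied. If the 0.48 is instead read as a lower hazard in the marker-absent chemotherapy cell, power is 73.4% without an arm effect and 69.1% with one. That reading does not reproduce the stated 80%.

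**What to change.** In Section 11.4:

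1. Replace the no-effect assumption with no interaction between marker and randomized arm, matching the main table and Appendix 18.2. Restate the interaction power as about 78% under an arm hazard ratio of 0.72.
2. Stratify the marker log-rank tests and Cox models by randomized arm.
3. Add one exploratory marker-by-arm interaction test for DFS per marker. Report it as hypothesis-generating, state the number of markers tested, and give the detectable ratios (about 2.1, 2.3 and 3.0 at 30%, 20% and 10% prevalence) before any multiplicity adjustment.

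A Mantel-Haenszel test by arm for nodal status, and arm as a term in the Appendix 18.2 prognostic models, are optional and change almost nothing.

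The cost is SAP wording and one extra exploratory test per marker, with no new patients, samples or assays. Section 15.0 makes the translational studies conditional on funding, so on these documents the wording can be settled before marker data exist.
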